11.1 Adverse Events

Adverse events will be coded using the Medical Dictionary for Regulatory Activities (MedDRA), Version 17.0 adverse events dictionary.

An AE (classified by preferred term) that occurs during the study will be considered a TEAE if:

- it has a start date and time on or after the first dose of investigational product and up to 7 days after the last dose of study drug, or
- it has a start date and time before the date and time of the dose of investigational product (i.e. it is part of the patient's medical history), but increases in severity on or after the date and time of the dose of investigational product.

Adverse events will be collected from the start of first dose until 1 week post-treatment visit, which is at 7±2 days after receiving the last dose of investigational product. All SAEs with an onset within 30 days after the last dose of investigational product will be collected. In addition, any related SAEs with an onset >30 days after last dose of investigational product will also be collected.

Any pre-treatment adverse event starting between the first date of the observation period to the administration of investigational product in Period 1 will be considered as medical history. Any AE starting after first dose of investigational product will be captured for this study.

An overall summary of TEAEs will be provided by treatment, by exposure, by time of onset, including the number and percentage of subjects who experience, and absolute count of events by treatment for:

- Any TEAE
- Any serious TEAE
- Any TEAE related to investigational product in the opinion of the investigator

- Any TEAE leading to dose discontinuation from the study
- Any severe TEAE.
- Any TEAEs leading to Death
- The number and percentage of subjects reporting TEAEs will be tabulated in the following ways:
 - By SOC, preferred term and treatment (including absolute count of events)
 - By SOC, preferred term, and maximum severity
 - By SOC, preferred term, and serious TEAE
 - By SOC and preferred term for TEAEs related to investigational product in the opinion of the investigator

For Serious AEs and AEs related to the investigational product if there are greater than 5 events, these will be tabulated by SOC and preferred term. For Serious AEs and AEs related to the investigational product, if there are less than or equal to 5 events, a listing will be provided. All information about AEs collected on the eCRF will be listed alongside the treatment, preferred term, and SOC.

To examine if the overall AE incidence varies as the weight adjusted dose increases, the overall summary of TEAE will be presented by weight-adjusted dose group (dose normalized to body weight [U/kg]). The adjusted dose is defined as period specific dose (500 U or 1000 U) divided by the period specific baseline weight (kg). Period specific baseline weight is the weight prior to the first dose in each treatment period. The adjusted dose will be spitted into 4 groups according to 25th, 50th and 75th percentiles of the adjusted dose.

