6.1 Medical History and Physical Examination

A medical history will be taken at the screening visit, and updated prior to randomization on Day 1 of Treatment Period 1 to ensure that the subject remains eligible for study participation.

All medical history findings that have been present/active within 1 year prior to enrollment will be recorded in the eCRF regardless of clinical relevance or presence at study start. Medical history findings that have not been present within 1 year prior to enrollment will be recorded if deemed clinically relevant by the Investigator to the conduct of the study. The medical history is to include any history of allergic reactions to drugs.

The Investigator or designee will perform physical examinations at the time points specified in [Schedules 2, 3, and 4](#). General physical examinations will be performed in accordance with standard practices at the study site. Clinically significant physical examination abnormalities observed prior to dosing with study drug also will be recorded in the medical history section of the eCRF. Any new or worsening clinically significant abnormality observed any time after the start of study drug administration should be recorded as an AE (see Section [9.0](#)).

Body weight and height will be measured at the time points specified in [Schedules 2 and 3](#). Measurements should be performed without shoes and underclothes only and measured by the same individual at each assessment time point (if possible).

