9.0 ADVERSE EVENTS

An AE is any untoward, undesired, unplanned clinical event in the form of signs, symptoms, disease, or laboratory or physiological observations occurring in a subject participating in a clinical study with study drug, regardless of causal relationship. An AE includes any condition that (1) was not present prior to study therapy but appeared following initiation of study therapy or (2) was present prior to study therapy, but worsened in severity and/or frequency following initiation of study therapy. **NOTE:** In this study, angioedema attacks after the first dose of study drug will be reported as AEs.

Adverse events will be monitored from the first dose of study drug in Treatment Period 1 through 1-week post-treatment. The Investigator will follow a subject with any AE until the event is either resolved or assessed as stable and, where appropriate, additional written reports

will be provided. The Investigator will evaluate and report the onset date, outcome, end date, duration (if <24 hours), severity (intensity), relationship to study drug, actions taken, and determination of seriousness for each AE. In addition, the Investigator will report if the AE onset occurred during study drug administration or within 24 hours following completion of study drug administration.

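### The SAP's treatment-emergent definition drops the frequency half of the protocol's worsening rule, so a frequency-only worsening kept under its pre-dose start date is left out of the TEAE tables

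*SAP*

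**What the plan says.** Protocol 9.0 defines an adverse event to include a condition that "was present prior to study therapy, but worsened in severity and/or frequency following initiation of study therapy". Severity and frequency have equal standing there.

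SAP 11.1 gives two alternative routes to treatment-emergent status:

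- First condition: "it has a start date and time on or after the first dose of investigational product", with a window that closes 7 days after the last dose. Neither severity nor frequency matters here.
- Second condition: the event began before dosing, as part of the medical history, "but increases in severity on or after the date and time of the dose of investigational product".

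The same section assigns events that begin between the start of observation and dosing "in Period 1 will be considered as medical history", and adds: "Any AE starting after first dose of investigational product will be captured for this study".

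SAP 17, which lists changes from the protocol, mentions only the analysis populations.

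**The concern.** The two documents use different tests for the same thing. A child with a known recurrent complaint who has it more often on study drug, at the same intensity, has an adverse event under the protocol. Under the SAP's second condition that child has no treatment-emergent event.

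This matters because every adverse event table in SAP 20.1 (Tables 4.2.1 to 4.3.2) is restricted to treatment-emergent events, as is Listing 7.1.3 of related events. Table 4.2.5, which summarises events by weight-adjusted dose, is among them. Safety and tolerability of the two doses is a secondary objective. Within each dose the omission can act in one direction only: it can lower the reported incidence but never raise it.

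**Working it through.** The documents give no figure to reproduce, so the check sets the texts side by side and follows a frequency-only worsening through them.

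**Step 1. Compare the tests for a condition present before dosing.**

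| Change after first dose | AE under Protocol 9.0 | TEAE under the second condition of SAP 11.1 |
|---|---|---|
| Severity rises | Yes | Yes |
| Severity and frequency rise | Yes | Yes |
| Frequency alone rises | Yes | No |

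Only the last row differs.

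**Step 2. Ask which start date the record carries.** Protocol 9.0 says "The Investigator will evaluate and report the onset date, outcome, end date", among other items. Neither document says whether a worsened condition keeps its original onset or takes the date of worsening. Protocol 6.1 says "Any new or worsening clinically significant abnormality observed any time after the start of study drug administration should be recorded as an AE", but it does not settle the date either. The SAP does expect some adverse event records with a pre-dose start. The second condition has no purpose otherwise, and SAP 18.7 has a rule for missing severity in events that began before the first dose.

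**Step 3. Follow each way of recording it.**

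- (a) Original pre-dose start date kept: fails the first condition on date and the second because severity is unchanged. Not a TEAE.
- (b) Entered with onset at the date of worsening: meets the first condition. TEAE.
- (c) Entered as separate new episodes after first dose: each meets the first condition. TEAE.
- (d) Angioedema attacks: Protocol 9.0 says "In this study, angioedema attacks after the first dose of study drug will be reported as AEs". Each has a post-dose start and meets the first condition within its window. TEAE.

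Only (a) is lost.

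**Step 4. Find where case (a) is still reported.** It is absent from Tables 4.2.1, 4.2.2, 4.2.3, 4.2.4, 4.2.5, 4.3.1.1, 4.3.1.2 and 4.3.2, and from Listing 7.1.3. It appears in Listing 7.1.1, which covers all adverse events. It also appears in Listing 7.1.2 if it is serious or led to discontinuation.

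**Step 5. Size.** Twelve children are to be randomized and each is to receive both doses, so the intended denominator for each dose is 12. One omitted child changes a preferred-term row by 1/12 = 0.083, or 8.3 percentage points. The row for any TEAE changes only if that child has no other treatment-emergent event at that dose. This will be uncommon, because every post-dose attack counts. In the earlier open-label prevention study described in the protocol's pediatric experience section, 8 of 9 children aged 6 to 11 (89%) had at least one TEAE.

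**The case against.** The strongest reply is that the first condition already does most of the work. Adverse events are collected from first dose, and pre-dose events go to medical history. A careful site would enter a worsening with a post-dose onset. Recurrent complaints such as headache are episodic, so each recorded episode has its own start date. Pain at any location can also meet the protocol's definition of an attack (Protocol 6.10), and attacks after first dose are events in their own right. All of this stands, and it confines the gap to records that keep a pre-dose start. It does not close the gap, because neither document tells sites which date to use: two sites could record the same worsening differently and only one record would be counted.

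Second, the affected events are not hidden. Listings 7.1.1 and 7.1.2 carry them as described, and SAP 11.1 promises to tabulate or list serious and related events without restricting that sentence to treatment-emergent ones. This also stands, although the matching outputs in SAP 20 (Tables 4.2.3 and 4.3.2, Listing 7.1.3) are titled as treatment-emergent.

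Third, frequency is not among the items that Protocol 9.0 lists for each event, and Protocol 6.1 asks for no baseline frequency of medical history findings. Frequency worsening therefore rests on judgement. That is true, but the protocol's own definition already calls for that judgement. An adverse event record with a pre-dose start should exist only because the Investigator judged that the condition worsened.

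A reader might infer that every condition that becomes more frequent disappears from every TEAE table. Cases (b) to (d) show otherwise. A reader might also infer a distorted comparison of the doses. The same rule applies to both, and nothing in the documents shows that it favours either.

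**Conclusion.** Wrong as written, and minor. The SAP narrows the protocol's worsening criterion without declaring it. The consequence is limited to frequency-only worsening of a pre-existing condition recorded under its pre-dose start date. Such an event is left out of the TEAE tables and Listing 7.1.3, but it is still listed.

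The number of such events cannot be derived from the documents and is probably small. A reader might try to scale from the 50 TEAEs reported in the nine children aged 6 to 11 in the earlier prevention study. That needs a share of frequency-only worsening that the documents do not give. Exposure also differs: 828/9 = 92 infusions per child there, against 2 × 24 = 48 planned here. What can be said is the unit of loss, 8.3 percentage points per child in a preferred-term row, assuming all twelve children contribute to each dose.

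**What to change.** In SAP 11.1, change the second condition to read *increases in severity and/or frequency*. Any adverse event record with a pre-dose start that the Investigator reports as worsened after first dose then counts as treatment-emergent, and is assigned to the dose being given at the date of worsening.

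An equivalent route is to state that such worsening is entered as a new adverse event with onset at the date of worsening, so that the first condition captures it. This also supplies the date needed for dose assignment, since Protocol 9.0 lists an onset date but no separate date of worsening.

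The cost is one phrase and the matching derivation, or one recording instruction to sites. The second condition already needs a date of worsening for severity, so adding frequency brings no new kind of requirement. The small downside is reliance on the Investigator's judgement of frequency, because no separate frequency field is listed.

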11.2 Clinical Laboratory Variables

Descriptive statistics for clinical laboratory values (in SI units) and changes from baseline at each assessment time point will be presented by treatment for the following clinical laboratory variables.

Hematology:

Dosing Visits 1a (pre-dose), 12a, 1b (pre-dose), 12b, 24b, and 1-week post-treatment (or if prematurely discontinued): CBC consisting of WBC and differential counts and percentages, RBC count, hemoglobin, hematocrit, and platelet count.

Clinical Chemistry:

Dosing Visits 1a (pre-dose), 12a, 1b (pre-dose), 12b, 24b, and 1-week post-treatment (or if prematurely discontinued): Blood urea nitrogen (BUN), creatinine, glucose, sodium, potassium, chloride, carbon dioxide (CO₂), aspartate aminotransferase (AST), alanine aminotransferase (ALT), alkaline phosphatase (ALP), creatine phosphokinase (CPK), total bilirubin, calcium, phosphorus, total protein, and albumin.

Coagulation:

Dosing Visits 1a (pre-dose), 12a, 1b (pre-dose), 12b, 24b, and 1-week post-treatment (or if prematurely discontinued): Prothrombin time (PT), international normalized ratio (INR), and activated partial thromboplastin time (aPTT).

Virology:

Dosing Visit 1a (pre-dose) and 1-week post-treatment (or if prematurely discontinued): Human immunodeficiency virus (single assay antibody/Western Blot) and hepatitis (Hepatitis B Surface Antigen, Hepatitis C Antibody).

For all females who have reached menarche, urine pregnancy testing will be performed at the site at the time points specified in Schedules 2 and 4.

Clinical laboratory test values are potentially clinically important (PCI) if they meet either the low or high PCI criteria listed in Table 6 and fall outside the laboratory's normal range in the same direction (high or low) as their PCI criteria. Subjects with post-dose PCI values will be listed. A table will be provided for the shift from baseline to LAoT in clinical laboratory results for biochemistry, hematology, and Coagulation.

Table 6 Criteria for Potentially Clinically Important Laboratory Tests

Parameter	Age Range	Gender	Criteria for Clinically Significant Laboratory Abnormalities ^a	
			Low	High
Hematology				
Eosinophils (%)	All	Male, Female	NA	>4 x ULN
Hematocrit	All	Male, Female	<0.6 x LLN	>1.3 x ULN
Hemoglobin	All	Male, Female	<0.6 x LLN	>1.3 x ULN
Neutrophils (%)	All	Male, Female	<0.5 x LLN	NA
Platelets	All	Male, Female	<0.4 x LLN	>2 x ULN
Leukocytes (WBC)	All	Male, Female	<0.5 x LLN	>2 x ULN
Coagulation				
Prothrombin Intl. Normalized Ratio (INR)	All	Male, Female	NA	>1.5 x ULN
Activated Partial Thromboplastin Time (aPTT)	All	Male, Female	NA	>2.0 x ULN
Chemistry				
Albumin	All	Male, Female	<0.6 x LLN	NA

Table 6 Criteria for Potentially Clinically Important Laboratory Tests

Parameter	Age Range	Gender	Criteria for Clinically Significant Laboratory Abnormalities ^a	
			Low	High
Alkaline Phosphatase	All	Male, Female	NA	>3.0 x ULN
Alanine Aminotransferase (ALT)	All	Male, Female	NA	>3.0 x ULN
Aspartate Aminotransferase (AST)	All	Male, Female	NA	>3.0 x ULN
Bicarbonate	All	Male, Female	<0.5 x LLN	>1.3 x ULN
Total Bilirubin	All	Male, Female	NA	>1.5 x ULN
Blood Urea Nitrogen (BUN)	All	Male, Female	NA	>3.0 x ULN
Calcium	All	Male, Female	<0.7 x LLN	>1.3 x ULN
Chloride	All	Male, Female	<0.8 x LLN	>1.2 x ULN
Creatinine	All	Male, Female	NA	>1.5 x ULN
Potassium	All	Male, Female	<0.85 x LLN	>1.2 x ULN
Glucose	All	Male, Female	<0.6 x LLN	>3.5 x ULN
Sodium	All	Male, Female	<0.9 x LLN	>1.1 x ULN

NA=Not Applicable; LLN=Lower Limit of Normal; ULN=Upper Limit of Normal; Intl.=International.

^a If criteria in both directions are shown for a single parameter, then abnormalities in each direction are summarized separately.

11.3 Vital Signs

Descriptive statistics for vital signs (e.g. systolic and diastolic blood pressure and pulse) and their changes from baseline at each post-dose visit and final visit will be presented by treatment.

Vital sign values will be considered PCI if they meet the observed value criteria or the change from baseline criteria listed in [Table 7](#). A supportive listing of subjects with post-baseline PCI values will be provided. All vital signs results will be listed for the Safety Set.

Table 7 Criteria for Potentially Clinically Important Vital Signs

Vital Sign Parameter	Flag	Criteria
		Observed Value
Systolic blood pressure (mmHg)	High	Increase of ≥ 20 from baseline value and ≥ 140
	Low	Decrease of ≥ 20 from baseline value and ≤ 90
Diastolic blood pressure (mmHg)	High	Increase of ≥ 15 from baseline value and ≥ 90
	Low	Decrease of ≥ 15 from baseline value and ≤ 50
Pulse rate (beats per minute)	High	Increase of > 15 from baseline value and ≥ 100
	Low	Decrease of > 15 from baseline value and ≤ 45
Temperature ($^{\circ}\text{C}$)	High	> 38.3
	Low	< 35

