4.1 Inclusion Criteria

To be eligible for this protocol, a subject must:

1. Be a child (male or female), ≥ 6 to <12 years of age at the time of screening.
2. Have a confirmed diagnosis of Type I or Type II HAE and have a functional C1 inhibitor (C1 INH) level less than 50% of normal.
3. Have a history of ≥ 1.0 angioedema attacks per month (average) that are moderate¹ or severe² or require acute treatment³ during the 3 consecutive months prior to screening.
4. Agree to adhere to the protocol-defined schedule of assessments and procedures.
5. Have a parent(s)/legal guardian who is informed of the nature of the study provide written informed consent for the child to participate in the study before any study-specific procedures are performed (with assent from the child when appropriate).

Additional Inclusion Criteria (Qualifying for Randomization)

6. Have experienced ≥ 1.0 angioedema attacks per month (average) that are moderate¹ or severe² or require acute treatment³ during the 12-week baseline observation period.

¹ Moderate: Angioedema attack sign/symptom(s) interferes with the subject's ability to attend school or participate in family life and social/recreational activities.

² Severe: Angioedema attack sign/symptom(s) significantly limits the subject's ability to attend school or participate in family life and social/recreational activities.

³ 'Treatment' refers specifically to standard of care therapies used to treat an angioedema attack (e.g., C1 INH, kallikrein inhibitor, bradykinin receptor antagonist). Products used for the treatment of attack symptoms (e.g., analgesics, anti-emetics) do not qualify for this study inclusion criterion.

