6.2 Vital Signs

Blood pressure and heart rate will be measured at the time points specified in [Schedules 2, 3](#) and [4](#). Body temperature will be measured prior to randomization at Visit 1a. During the study, additional vital signs measurements will be performed if clinically indicated. Vital signs performed on dosing days should be obtained prior (within 60 minutes) to the start of the injection and between 10 to 30 minutes after completion of the injection of study drug. Every effort should be made to measure and record vital signs prior to any blood sample collection.

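### SAP Table 7 applies one unscaled set of vital-sign limits to children aged 6 to under 12, leaves its and/or rule unresolved, and has a temperature row with no scheduled post-baseline data

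*SAP*

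**What the plan says.** The trial enrols children only; Protocol 4.1 requires a subject to "Be a child (male or female), ≥ 6 to <12 years of age at the time of screening".

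SAP 11.3 defines PCI vital signs through Table 7, which does not vary by age, sex or height. Each blood pressure and pulse row holds two conditions in a single criteria column:

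- systolic high: "Increase of ≥ 20 from baseline value and ≥ 140"
- systolic low: "Decrease of ≥ 20 from baseline value and ≤ 90"
- diastolic high: "Increase of ≥ 15 from baseline value and ≥ 90"
- diastolic low: "Decrease of ≥ 15 from baseline value and ≤ 50"
- pulse low: "Decrease of > 15 from baseline value and ≤ 45"
- pulse high: a rise of more than 15 together with a value of at least 100

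The temperature row is purely absolute: above 38.3 °C or below 35 °C. The sentence introducing the table, however, treats the observed-value and change criteria as alternatives, joined by *or*. The supporting listing covers post-baseline values, and the planned output is Table 4.7.2.

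On temperature, Protocol 6.2 states: "Body temperature will be measured prior to randomization at Visit 1a". Schedules 2, 3 and 4 otherwise list vital signs as blood pressure and heart rate. Protocol 6.2 allows further readings when clinically indicated.

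Laboratory flags work differently. Table 6 uses multiples of the laboratory's lower or upper limit of normal, and SAP 11.2 also requires a value outside the "normal range in the same direction (high or low) as their PCI criteria".

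**The concern.** Safety and tolerability of the two dose levels is a secondary objective, and the PCI output is meant to pick out individual children whose readings moved by an important amount. A joint rule does that only if its level sits at a sensible distance from where the children start. If resting blood pressure lies well below 140/90 and resting pulse well above 45, the level decides the flag and the stated change plays no part. If the rule is read as *or*, the problem moves to the other rows: a child who normally sits at a limit is flagged without having changed.

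The temperature row raises a different problem. With no planned post-baseline readings, an empty row could be taken to mean that no child had a fever, when it would mean that temperature was not routinely taken.

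**Working it through.** The plan states no expected flag rate for Table 7, so there is no figure to reproduce. The limits below come from Table 7. The resting ranges are assumptions, because the documents contain no paediatric vital-sign values: systolic 90–110 mmHg, diastolic 55–70 mmHg, pulse 80–100 bpm.

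**Reading 1: both conditions required (*and*).** Let *b* be baseline, *d* the stated change and *L* the level. The change needed is max(*d*, *L* − *b*) for a high row and max(*d*, *b* − *L*) for a low row. The break-even baseline is *L* − *d* (high) or *L* + *d* (low). For the pulse rows, more than 15 is taken as 16 whole beats when computing the change needed; break-evens use 15.

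| Row | Break-even baseline | Change needed over the assumed range | Stated change |
|---|---|---|---|
| Systolic high | 140 − 20 = 120 | 140 − 110 = 30 to 140 − 90 = 50 mmHg | 20 |
| Diastolic high | 90 − 15 = 75 | 90 − 70 = 20 to 90 − 55 = 35 mmHg | 15 |
| Pulse low | 45 + 15 = 60 | 80 − 45 = 35 to 100 − 45 = 55 bpm | >15 |
| Systolic low | 90 + 20 = 110 | 20 mmHg throughout | 20 |
| Diastolic low | 50 + 15 = 65 | 15 mmHg up to baseline 65; 70 − 50 = 20 at 70 | 15 |
| Pulse high | 100 − 15 = 85 | 100 − 80 = 20 at 80; 16 bpm from 85 | >15 |

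The break-evens follow from Table 7 alone. In the first three rows the whole assumed range lies on the side where the level governs, so the stated change never decides the flag. The last three rows work at or close to their stated change.

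**Reading 2: either condition sufficient (*or*).** A change of 20 mmHg systolic, 15 mmHg diastolic or more than 15 bpm flags at any baseline, which removes the insensitivity in the first three rows. But the level alone now also flags. A child resting at systolic 90 and measured at 90 has changed by 90 − 90 = 0 and is flagged low. A child resting at pulse 100 and measured at 100 has changed by 0 and is flagged high. Both values are edges of the assumed ranges.

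**Temperature.** Scheduled readings: one, before randomization at Visit 1a. Scheduled post-baseline readings in Schedules 2 to 4: zero. SAP 18.3 uses all post-baseline assessments for PCI determination, so the row can be filled only by unscheduled, clinically indicated readings. This step needs no assumption.

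**The case against.** A reader might infer that Table 7 leaves high blood pressure, slow pulse and fever after infusion almost impossible to flag, and that this is the trial's only check on them. The documents do not support that.

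- The blood pressure and pulse rows are not bare cut-offs. Each includes a change from the child's own baseline.
- The insensitivity belongs to the *and* reading. The *or* in SAP 11.3 would remove it for high blood pressure and low pulse. This stands, but it does not rescue the table, because unscaled levels then flag unchanged children.
- The weakness is one-sided. Low systolic is not insensitive over the assumed range, and low diastolic is not at baselines up to 65. Nor does the *and* rule clearly over-flag fast pulse: a trigger at 16–20 bpm is close to the stated change.
- Other safeguards remain: change-from-baseline summaries by treatment (Table 4.7.1), the full listing (Listing 8.2), an adverse event definition that includes physiological observations (Protocol 9.0), and ongoing review by the medical monitor (Protocol 10.0). With twelve subjects the listing can be read child by child, although it applies no flag.
- A febrile child could be measured if clinically indicated, and the fever reported as an adverse event. The defect is an ambiguous row, not suppressed detection.
- Table 6 is an imperfect model. It lists age as all and both sexes together, and the documents do not say that its normal ranges are age- or sex-specific. It shows only that the SAP ties laboratory flags to a reference range and vital-sign flags to none.

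PCI flags drive no stopping rule (Protocol 5.5) and no monitoring committee review (SAP 15), which limits the consequence.

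**Conclusion.** The point holds in limited form. The absence of age scaling, the and/or contradiction, the break-even baselines of 120, 75 and 60, and the lack of scheduled post-baseline temperature are all established from the documents. How far the high blood pressure and low pulse rows depart from their stated changes rests on the assumed resting values and on the *and* reading; how often the *or* reading would flag an unchanged child likewise depends on actual resting values. Unscaled levels can therefore misclassify under either reading, in different rows.

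The consequence is confined to which children appear in Table 4.7.2 and its supporting listing. The primary analysis and the sample size are untouched. It is a cheap improvement to a descriptive safety output and should be made before the outputs are produced.

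**What to change.** Three edits to SAP 11.3:

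1. State one rule, *and* or *or*, and make the sentence and the Table 7 rows agree.
2. Replace the absolute blood pressure and pulse levels with age-appropriate reference limits from a source named in the SAP, and keep the change-from-baseline part.
3. Delete the temperature row, or label it as applying to unscheduled readings only, so that an empty row is not read as absence of fever.

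The cost is a table edit, a programmed look-up of reference limits and somewhat more flags to review. New scheduled temperature readings would require a protocol change and are not needed to resolve this point.
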